## Study Protocol

The second year of "A Trauma-Informed Approach for Positive Youth Development for Montana Students" will continue in the same format as winter 2020, but with 35 participants in an experimental group, along with 20 students in a control group within the same school and enrolled in classes by the same physical education teacher. District leaders wish to hold the study during the Jan-March 2021 window, as this timeframe has shown a historical spike in inappropriate student behaviors and absenteeism. Twice weekly 45-minute sessions during the 8-week intervention period will occur within two physical education classes in order to draw enough participants to gauge statistical significance with resulting data; a third physical education class with the same teacher will serve as the control group for the study, therefore creating 3 gym class clusters, which will allow for computer-generated randomization. Instead of individuals being randomly assigned, gym class clusters of individuals will be randomly allocated to intervention groups. Control group participants will also be offered 8 weeks of yoga after the study concludes.

Student incentives for at least a 75% attendance record in the experimental group include receiving a Fitbit Inspire HR for the study to track their physical health data and students will retain these to encourage healthy exercise and sleep patterns following the study. Teacher incentives for completion of surveys include classroom supply money (funneled through school administration). Gift cards will be provided to parents/guardians who complete the surveys about their child; these will be disseminated by school officials for parents to pick up at the high school, or they may be mailed by the PI on request. Control group participants will also each receive Fitbit Inspire HR upon completion of all pre- and post-survey measures as an incentive.

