### **Statistical Analysis Plan**

Gym class clusters of individuals will be randomly allocated to intervention groups. This approach is necessary because randomization at the individual level is impractical and we strive to avoid contamination between treatment groups. The responses from individuals within a cluster are likely to be more similar than those from different clusters because individuals within a will share a common yoga class experience. This lack of independence introduces complexity to the design and analysis. The degree of similarity, or clustering, will be quantified and reported using the intraclass correlation coefficient (ICC). When the ICC is low, individual observations contribute nearly equally to the analysis. (38). For all participants, baseline surveys (see table above) will be conducted prior to exposure to Yoga (T0). Follow-up surveys will be collected at 8 weeks (T1). Analyses will be conducted using R Version 3.6. Baseline differences between intervention and control group will be examined using independent *t* test or  $\chi^2$  test. All data will be analyzed according to treatment assignment. Two strategies will estimate treatment effects: 1) Cluster level analysis using summary measures; and 2) Individual level analysis adjusted for clustering to appropriately account for the nested structure of data and cluster randomization in

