estimating. For the first, we will measure mean outcomes by cluster followed by parametric t-tests or non-parametric tests, depending on the distributions of the outcome measures. To account for the variability between gym classes and nested structure of the data, multilevel mixed-effects models will be used for each continuous outcome, with time (T0 & T1) as level 1, students as level 2, and class as level 3. To adjust for baseline pre-treatment values, explanatory variables for each outcome will include grade, gender, prior exposure to yoga at the high school, and survey time point (model 1). To assess the intervention's effect on outcomes, we will use condition (intervention or control) and the interaction between condition and time as predictors (model 2). Effect sizes (ESs) will be calculated as (estimated intervention effect)/ $\sqrt{\text{variance at student level}}$ . Interpretation of ES will determine the gains of the intervention versus control group. To calculate power for this cluster randomized trials that compares two means, we used the "clusterPower" package in R (24). Accounting for clustered design effects, 55 participants with variation in cluster sizes, an assumed low intraclass correlation of 0.001, and within-cluster variation of 5 units, this would provide at least 65% power to detect clinically meaningful effects between the treatment and control arm using two-sided tests at  $\alpha=0.05$ . To maximize test power and precision of estimation considering the few clusters in this study, we will also use wild cluster bootstrap-t procedure to correct our standard errors (9, 47).

A proxy for improved well-being, secondary academic performance outcomes, will also be analyzed descriptively pre- (during week 1) and post-intervention (at the end of week 8) (see table above).

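### Prior school yoga, grade and gender enter only as time-constant main effects, so with complete pairs they cannot adjust the condition-by-time estimate

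*Combined protocol and SAP*

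**What the plan says.** The Statistical Analysis Plan specifies a three-level mixed model "with time (T0 & T1) as level 1, students as level 2, and class as level 3". Under the stated aim "To adjust for baseline pre-treatment values", it says that "explanatory variables for each outcome will include grade, gender, prior exposure to yoga at the high school, and survey time point (model 1"). For the intervention effect, "we will use condition (intervention or control) and the interaction between condition and time as predictors (model 2"). No product of time with prior yoga, grade or gender is listed. The plan does not say whether model 2 keeps the model 1 covariates, how prior exposure is recorded, or how common it is in each class.

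The other estimation strategy is a cluster-level one, in which "we will measure mean outcomes by cluster followed by parametric t-tests or non-parametric tests". It names no covariates.

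Two further statements bear on prior exposure. The Study Protocol section says that the second year "will continue in the same format as winter 2020". The Statistical Analysis Plan says that, for all participants, "baseline surveys (see table above) will be conducted prior to exposure to Yoga (T0").

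**The concern.** The investigators chose prior school yoga as an adjustment variable, so they evidently regard it as a possible source of difference between students. Only three classes are allocated, two to yoga and one to control, so randomisation gives little assurance that prior exposure will be balanced. If students with earlier yoga change differently over the eight weeks, for whatever reason, an imbalance passes into the yoga-versus-control contrast. The report would then describe that contrast as adjusted for prior yoga when the adjustment had not touched it. The same holds for grade and gender.

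The definition of T0 adds a smaller difficulty. Taken literally, a baseline before any yoga cannot apply to a student who is positive on the prior-exposure covariate.

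**Working it through.** **Inputs from the documents.** Two occasions; 35 yoga and 20 control students; three classes; the model terms quoted above. The documents give no figure on prior yoga, so there is none to reproduce. The stated power does not bear on this point.

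**Assumed inputs.** Prior yoga in 40% of the yoga arm (14/35) and 10% of the control arm (2/20), and the effects shown below.

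**Step 1: what a main effect can do.** For student i, let C be condition, x prior yoga, u the student intercept and c the class intercept:

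- T0: y = a + u + c + γx + δC + e0
- T1: y = a + τ + u + c + γx + δC + θC + e1
- Change: D = τ + θC + (e1 − e0)

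The terms γx, u and c have gone. With complete pairs the estimate of θ is mean D in the yoga arm minus mean D in the control arm, whether or not x is in the model. In simulated fits (35 v 20, student intercept) the estimates with and without the three covariates agreed to within 2e-14 in every data set. With 15% of T1 values missing at random (assumed), single data sets differed by up to 0.11 to 0.20, and the averages by about 0.01 or less.

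**Step 2: what remains.** Let prior yoga shift the outcome by λ at T0 and by λ + κ at T1. Then D = τ + θC + κx + error, and

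bias in θ = κ × (share with prior yoga in yoga arm − share in control arm).

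λ does not appear. Simulated means, true effect −2, 40 data sets per row:

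| Assumed effect of prior yoga | Shares | Predicted bias | No covariates | Main effects | Plus prior yoga × time |
|---|---|---|---|---|---|
| −2 at both occasions | 40% v 10% | 0 | −2.00 | −2.00 | −2.02 |
| Change altered by +1.5 | 40% v 10% | 1.5 × 0.30 = 0.45 | −1.54 | −1.54 | −2.00 |
| Change altered by +1.5 | 40% v 40% | 0 | −1.93 | −1.93 | −1.93 |
| −2 at T0, half faded by T1 | 40% v 10% | 1 × 0.30 = 0.30 | −1.66 | −1.66 | −1.98 |

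**Step 3: the two remedies.** Take a 3-point effect on change, the same shares and no true yoga effect, so the predicted bias is 3 × 0.30 = 0.90. With student and residual SDs of 3.5 (assumed), regressing T1 on T0 and the covariates brought the bias from 0.90 to about 0. Its estimates had SD 1.26, against 1.44 for the change model with prior yoga × time. The two sets of estimates correlated 0.85, so they are different analyses.

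**Step 4: cost in precision.** For a binary covariate in a change model, the information on condition is the sum over strata of n1·n0/(n1 + n0).

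- No covariate: 35 × 20/55 = 12.73.
- Prior yoga 14/35 v 2/20: 21 × 18/39 + 14 × 2/16 = 9.69 + 1.75 = 11.44. SE ratio √(12.73/11.44) = 1.05. In simulation with the 3-point effect the net rise was about 2% (1.42 to 1.45), because the term also explains some residual variation.
- A grade split of 31/35 v 2/20 (assumed): 31 × 2/33 + 4 × 18/22 = 1.88 + 3.27 = 5.15. SE ratio √(12.73/5.15) = 1.57.

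**Step 5: if prior yoga only modifies the response to yoga.** Assume an effect of −2 in naive students, −0.5 in experienced students, and no change in controls.

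- Plan's estimate: (14 × −0.5 + 21 × −2)/35 = −1.40, the average effect in the yoga arm.
- Whole-sample average: (16 × −0.5 + 39 × −2)/55 = −1.56.
- With prior yoga × time: (9.69 × −2 + 1.75 × −0.5)/11.44 = −1.77, further from both.

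**The case against.** The strongest reply is that condition by time already removes the ordinary form of carry-over. A student who still practises earlier techniques does so at both T0 and T1, and the first row of the table shows no bias. That stands.

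Other mechanisms, such as faster uptake or less room to gain from yoga, act mainly in students now receiving yoga. They are effect modification, and Step 5 shows that a prior-yoga-by-time term can then move the estimate away from the average effect. That also stands, and it is why the term belongs in a sensitivity analysis.

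Allocation is computer-generated, so any imbalance is due to chance, and the planned baseline comparisons could expose it. This is fair as far as it goes, but exposing an imbalance does not correct it, and three classes leave much to chance.

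The main effect is also not wholly inert. Besides its small influence when T1 is missing, it can alter the reported effect size, whose denominator is student-level variance. In the first table row that variance fell from 3.15 to 2.28, which enlarges the effect size by √(3.15/2.28) − 1, about 18%, for the same estimate. This does not restore the adjustment: a covariate that rescales the effect size without changing the contrast has removed no confounding.

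Finally, the T0 wording can reasonably be read as before this intervention. It needs clarifying and is not a substantive contradiction.

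**Conclusion.** The point holds in a limited form. As listed, the covariates cannot adjust condition by time when pairs are complete. They therefore give no protection against prior yoga altering the T0-T1 change where exposure differs between arms. This follows from the model, whether or not model 2 retains the model 1 covariates.

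The size of any bias is unknown. It is the product in Step 2, and both factors are assumed: 0.45 points in the unfavourable case tabulated, and nil under balance or constant carry-over.

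A reader might infer that all carry-over from earlier yoga stays in the treatment effect. The documents do not support that, because the stated estimand is a difference of changes. Constant carry-over would survive only if the cluster-level comparison used T1 means alone (simulated mean −2.54 against a true −2), and the plan does not say that it does. Nor do the documents show that experienced students are present in either arm or are unevenly distributed; they only name the covariate.

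**What to change.** 1. Estimate the effect by regressing T1 on condition, T0 outcome, prior yoga, grade and gender, keeping the planned correction for clustering. Alternatively, keep model 2 and add prior yoga × time as a pre-specified sensitivity analysis. Name one as the main analysis, since the two can give different answers.
2. State whether model 2 retains the model 1 covariates, define prior school yoga, and tabulate it by class.
3. Reword the sentence defining T0 so that it means before this year's yoga.
4. Label any estimate in yoga-naive students as exploratory. If prior yoga changes only the response to yoga, neither model removes that.

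The cost is SAP wording and at most one extra model term, using a variable already planned. Under the assumed 40% v 10% split, prior yoga × time raises the SE by about 2% in the simulation, or about 5% if the term explains no variation in change. It also relies on prior exposure varying within classes. Grade × time should not be required: if grade and class nearly coincide it could inflate the SE substantially, by about 57% in the assumed split.

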### ***Salivary Cortisol Assays.***

Students in both the experimental and control groups will be administered cortisol testing at the beginning of weeks 1 and 4 and the conclusion of week 8, each time prior to the yoga session (or at the beginning of their physical education class, if in the control group). Specifically, students will provide a saliva sample to the school nurse or PI, to be deidentified (using a code key system) before analysis by the CAIRHE Translational Biomarkers Core Lab at MSU. Testing will use the Abcam (ab154996) cortisol in vitro competitive ELISA (Enzyme-Linked Immunosorbent Assay) kit designed for accurate quantitative measurement of cortisol in saliva (sensitivity 0.12 ng/ml). Deidentified cortisol data will be returned to the PI for re-identification using the code key. Comparisons using paired t tests will assess trends and determine usefulness of this measure.

---

 If we increase  $\alpha$  to 0.1, we can reduce the probability of a **Type II error** and increase our power to 0.86 but we are also more likely to commit a **Type I error** (rejecting a true null hypothesis).

Using deidentified participant codes (with the PI retaining access to the code key system), data will be triangulated through observational data, qualitative remarks in participant journals, pre- and post-survey data, heart rate and sleep cycle data, cortisol analyses, and secondary academic and behavioral data.

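### The 65% power figure rests on an unsourced ICC of 0.001 that all but removes clustering; with respect to the ICC it is close to a ceiling, not a minimum

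*Combined protocol and SAP*

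**What the plan says.** The Study Protocol section describes three gym classes allocated as clusters: two receive yoga (35 students) and one is the control (20 students).

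The Statistical Analysis Plan explains why clustering matters: "The responses from individuals within a cluster are likely to be more similar than those from different clusters". It says that this complicates design and analysis, and that the ICC will be estimated and reported. It gives no expected size for the ICC.

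The power statement in the same section uses 55 participants, "an assumed low intraclass correlation of 0.001" and a within-cluster variation of 5, and concludes that "this would provide at least 65% power to detect clinically meaningful effects", "using two-sided tests at" alpha 0.05. Footnote 1, printed under Salivary Cortisol Assays, says that raising alpha to 0.1 would "increase our power to 0.86". The documents give no numeric difference, no named outcome, no source for the ICC and no power at any other ICC. They do not say whether the 5 is a variance or a standard deviation.

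**The concern.** An ICC of 0.001 with classes of about 17 to 20 is almost the same as assuming independent students. The plan first argues that independence cannot be assumed, then computes power as if it nearly could, and words the result as a minimum. With only three classes, and a single class in the control arm, between-class variance passes almost undiluted into the arm difference, so power is sensitive to this one input.

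What is at stake is how the result is read. The Study Protocol section links the use of two yoga classes to having enough participants for a significance test, and Aim 1 says effectiveness will be assessed. A reader who takes 65% as a floor would give a null result more weight than the design can bear.

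**Working it through.** **Inputs from the documents.** 35 against 20 students; three classes, two against one; ICC 0.001; two-sided alpha 0.05; power 65%; 0.86 at alpha 0.1.

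**Assumptions of this review.** Yoga classes of 17 and 18; total variance fixed at 1, so effects are in SD units; ICC values from 0 to 0.10; cluster-level degrees of freedom equal to classes minus arms.

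**Step 1: the plan's own figure.** The 65% cannot be reproduced forward, because no difference is stated. It can only be back-solved.

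- Variance of a class mean of size k: v_k = ICC + (1 − ICC)/k.
- Variance of the arm difference: (v17 + v18)/4 + v20 = 1.5 × ICC + (1 − ICC) × 0.0786, where 0.0786 = (1/17 + 1/18)/4 + 1/20.
- At ICC 0.001: 0.0015 + 0.0785 = 0.0800, so SE = 0.283. The design effect is 0.0800/0.0786 = 1.018.
- 65% power under normal theory needs effect/SE = 2.345, so the effect is 2.345 × 0.283 = 0.66 SD.

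**Step 2: hold 0.66 SD fixed and change only the ICC** (normal theory, alpha 0.05).

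| ICC | Design effect | SE | Effect/SE | Power |
|---|---|---|---|---|
| 0 | 1.00 | 0.280 | 2.37 | 66% |
| 0.001 | 1.02 | 0.283 | 2.35 | 65% |
| 0.01 | 1.18 | 0.305 | 2.18 | 59% |
| 0.02 | 1.36 | 0.327 | 2.03 | 53% |
| 0.05 | 1.90 | 0.387 | 1.71 | 40% |
| 0.10 | 2.81 | 0.470 | 1.41 | 29% |

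Removing clustering altogether gains less than one point (65.8%), and every ICC above 0.001 loses power. Yoga classes of 22 and 13 change these figures by less than one point. Holding within-class rather than total variance fixed gives slightly lower values (39% at ICC 0.05, 27% at 0.10).

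**Step 3: the footnote on the same basis.** Back-solving to 86% at alpha 0.1 and ICC 0.001 gives 2.725 × 0.283 = 0.77 SD. Power for that effect is 81%, 76%, 64% and 50% at ICC 0.01, 0.02, 0.05 and 0.10.

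**Step 4: do 65% and 0.86 belong together?** This question is separate from the ICC. The effect that gives 65% at alpha 0.05 gives, at alpha 0.1:

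| Basis | Power at alpha 0.1 |
|---|---|
| Normal theory | 76% |
| t, 4 df | 82% |
| t, 3 df | 84% |
| t, 2 df | 87% |
| t, 1 df | 94% |

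Only 2 df comes within 2 points of 0.86. Two degrees of freedom correspond to four classes (4 − 2); the planned three classes leave 3 − 2 = 1.

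**Step 5: what that difference costs.** With four equal classes of 55/4 = 13.75, the variance of the difference at ICC 0.001 is 0.001 + 0.999/13.75 = 0.0737, so SE = 0.271. On 2 df, 65% power needs effect/SE = 4.526, so the effect is about 1.23 SD. In the three-class layout the same effect gives 1.23/0.283 = 4.34, against a critical t of 12.71 on 1 df. Power is about 27%, with the ICC still at 0.001.

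**The case against.** **The two statements do not contradict each other.** A reader might infer that 0.001 contradicts the plan's remarks on clustering. It does not: 0.001 is positive, the plan labels it an assumed low value, and the text gives no magnitude. The two are in tension, and the value is unjustified. One school and one teacher for all three classes could also lower between-class variance.

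**No usual ICC is given.** A reader might infer that power is far lower at the ICC to be expected in school classes. The documents contain no such figure. At 0.01 the loss is about 6 points; only from about 0.05 is it large.

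**The claim of a minimum could refer to the effect.** It could mean effects of a given size or larger. With no size stated, that reading cannot be checked, and it would not make the figure a minimum over the ICC.

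**The planned model differs from the powered test.** Model 2 tests condition by time. A stable class effect cancels from that contrast, and only class-by-time variation inflates it. This limits how far the percentages carry over. It does not rescue the power statement, which is itself for a comparison of two means.

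**The 27% is not an ICC effect.** It arises at ICC 0.001 and comes from the degrees of freedom. It also depends on reading the 65% as about 65%. If the true figure were well above that, the pair could be reconciled otherwise: under normal theory 86% at alpha 0.1 corresponds to 78% at alpha 0.05 (2.725 − 1.960 = 0.765).

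**Clustering is handled at analysis.** The plan commits to cluster-level summaries, a three-level model and a wild cluster bootstrap. A reader might infer that a low estimated ICC would be used to ignore clustering; the plan says only that the ICC will be reported. These methods do not, however, validate the ICC used for planning.

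**It is a pilot that openly states 65%.** That is fair and limits the consequence, but a stated power should still be described correctly.

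**Conclusion.** The point stands in this form: both power figures rest on an unsourced ICC that makes clustering negligible, no sensitivity is shown, and the claim of a minimum points the wrong way with respect to the ICC. That last conclusion needs no choice of ICC, since the most that can be gained is under one point. The size of the loss does depend on that choice: 65% becomes 59% at ICC 0.01, 40% at 0.05 and 29% at 0.10. Those figures are relative to a back-solved 0.66 SD and apply to the two-mean comparison.

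A second, separate problem is that the 65%/0.86 pair, taken at face value, fits about 2 degrees of freedom and not the 1 that three classes leave. How the authors obtained the pair cannot be confirmed from the documents.

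The documents do not support saying that the plan contradicts itself, or that the true power is any particular lower value.

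**What to change.** In the power statement of the Statistical Analysis Plan:

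1. Delete the words that present 65% as a minimum.
2. Name the outcome and the difference to be detected, and say whether the 5 units are an SD or a variance.
3. Give the basis for the ICC, or say that there is none.
4. Replace the single figure with power for the actual three classes, two against one, over a stated ICC range such as 0.001 to 0.10. State the degrees of freedom used.
5. Recompute the 0.86 in footnote 1 on the same basis.

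This is a text change that needs no extra students and no change to the design. The cost is that the stated power becomes less favourable.

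### The stated powers (at least 65% at alpha 0.05, 0.86 at alpha 0.10) cannot both hold for a class-level comparison of three classes, which has 1 degree of freedom

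*Combined protocol and SAP*

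**What the plan says.** The Study Protocol section places yoga in two physical education classes (35 students) and uses a third class with the same teacher as control (20 students), "therefore creating 3 gym class clusters, which will allow for computer-generated randomization". The unit of allocation is explicit: "Instead of individuals being randomly assigned, gym class clusters of individuals will be randomly allocated to intervention groups". The same section says that two yoga classes are used "in order to draw enough participants to gauge statistical significance with resulting data".

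The Statistical Analysis Plan sets out two strategies. In the first, "we will measure mean outcomes by cluster followed by parametric t-tests or non-parametric tests". The second is a multilevel model with time, student and class as levels, and because clusters are few, "we will also use wild cluster bootstrap-t procedure to correct our standard errors".

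Power was computed with the clusterPower package in R for 55 participants in clusters of varying size, with "an assumed low intraclass correlation of 0.001, and within-cluster variation of 5 units". The claim is that "this would provide at least 65% power to detect clinically meaningful effects between the treatment and control arm using two-sided tests" at alpha 0.05. Footnote 1, printed under Salivary Cortisol Assays, says that alpha 0.10 would "increase our power to 0.86".

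The plan does not give the number of classes per arm entered in the software, the degrees of freedom, the difference to be detected, or whether 5 is a variance or an SD. It also does not say which of the two strategies the power refers to.

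**The concern.** In a cluster-randomised comparison, the error term for the arm effect is variation between clusters. Three class means in two arms leave one degree of freedom to estimate it, and that one comes entirely from the difference between the two yoga classes. The two-sided critical value at 0.05 is then 12.706, against about 2 for a test that treats the 55 students as independent. A power of 65% looks implausible for such a test unless the effect is very large, and the alpha 0.10 figure gives a way to check it.

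What is at stake is how the between-arm results are read. The protocol justifies its layout by the aim of testing significance, and the SAP backs this with a formal power figure. A null result could be taken as evidence from a moderately powered comparison when the class-level test had little chance of detecting an ordinary effect.

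**Working it through.** **Inputs from the documents.** Two yoga classes and one control class; 35 and 20 students; t-test on class means; ICC 0.001; power at least 0.65 at two-sided 0.05; power 0.86 at 0.10.

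**Reproducing the plan's figures.** Neither power can be recomputed alone, because no difference is stated. The pair can be tested. For a t-test with ν df, power = P(|T′(ν, λ)| > t(1-α/2, ν)), where λ = difference / SE. Changing alpha changes only the critical value; λ stays the same. So I solve for the λ that gives one stated power and read off the other.

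| df | λ for 65% at 0.05 | implied power at 0.10 | λ for 0.86 at 0.10 | implied power at 0.05 |
|---|---|---|---|---|
| 1 | 11.912 | 0.938 | 9.434 | 0.541 |
| 2 | 4.526 | 0.871 | 4.426 | 0.634 |
| 3 | 3.493 | 0.836 | 3.639 | 0.682 |
| 4 | 3.115 | 0.816 | 3.343 | 0.708 |
| 53 | 2.389 | 0.762 | 2.761 | 0.773 |

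The stated pair is at least 0.65 and 0.86. With 1 df it misses by about 8 points in one direction (0.94 against 0.86) and 11 in the other (0.54 against 0.65). Rounding does not explain this: 0.855 to 0.865 at alpha 0.10 gives 0.535 to 0.547 at 0.05. Nor do one-sided tests (0.935 and 0.545).

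**Hand check of the 1-df row.** When λ is large, 1-df power is close to 2Φ(λ/t) - 1, where t is the critical value: 12.706 at 0.05 and 6.314 at 0.10.
- From 65%: λ/12.706 = 0.935, so λ ≈ 11.9. Then 11.9/6.314 = 1.88 and the power is 0.94.
- From 0.86: λ/6.314 = 1.476, so λ ≈ 9.32. Then 9.32/12.706 = 0.733 and the power is 0.54.

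**What the figures may have assumed.** If 65% is the computed value, about 2 df fits (0.871 at 0.10), which is what two classes per arm would give. If 65% is a loose floor, 3 or more df fits, as does an individual-level calculation (0.86 goes with 0.77). The documents do not show which was used.

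**Size, as illustration only.** Assumed class sizes are 17.5, 17.5 and 20, and effects are in within-class SDs. With v = ICC/(1 - ICC), SE = √[(v + 1/17.5)/2 + v + 1/20]. At ICC 0.001 this is √(0.02907 + 0.05100) = 0.283. ICCs above 0.001 are also assumptions.

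| ICC | SE | power at 0.05 for 0.5 / 0.8 / 1.0 SD | effect needed for 65% |
|---|---|---|---|
| 0.001 | 0.283 | 11% / 18% / 22% | 3.4 SD |
| 0.01 | 0.306 | 11% / 16% / 20% | 3.7 SD |
| 0.05 | 0.397 | 9% / 13% / 16% | 4.7 SD |
| 0.10 | 0.495 | 7% / 10% / 13% | 5.9 SD |

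The last column is 11.912 × SE. The 95% CI half-width at ICC 0.001 is about 12.71 × 0.283 = 3.6 SD, if the class-level SD is estimated at its expected value. An effect that would give 65% with four classes and 2 df (1.07 to 1.23 SD, depending on class size) has 23% to 27% power with the actual three classes. One that would give 65% at individual level (about 0.67 SD) has about 15%.

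The noncentral t treats the class means as equally variable. Simulating the class-mean t-test with classes of 17, 18 and 20 gave 25.5% for the 1.23 SD effect, against 26.7% from the formula.

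**Smallest attainable p-values in the other planned tests.**
- Exact rank-sum test, 2 v 1: the control class takes rank 1, 2 or 3 with probability 1/3 each. Both end ranks count as extreme, so the minimum two-sided p is 2/3.
- Permutation test on the difference in means: three allocations, so the minimum is 1/3.
- Wild cluster bootstrap-t with +1/-1 weights and the null imposed (both assumed; the SAP specifies neither): 2³ = 8 sign patterns. The all-plus and all-minus patterns give the observed |t|, so the minimum is 2/8 = 0.25.

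**The case against.** The strongest reply is that the SAP never ties its power to the t-test on class means. The sentence follows the mixed-model text and mentions a clustered design effect, so it may describe the individual-level strategy. At 53 df, 0.86 at alpha 0.10 goes with 0.77 at 0.05, which does satisfy a floor of 65%. That stands as a possible origin of the numbers. It does not make them valid for this trial: such a calculation treats the between-class variance as known (ICC exactly 0.001), while the three randomised classes leave 1 df to estimate it.

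A second reply is that either power alone can be reached with 1 df if the effect is large enough (about 3.4 SD for 65%, 2.7 SD for 0.86 at alpha 0.10). That is correct. Only the pair is impossible, and the documents do not show which figure is wrong. The 54% follows only if 0.86 is right; if 65% is right, footnote 1 understates power. The qualifier on the 65% does not help, because a higher value at 0.05 pushes the 0.10 value above 0.94.

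Finally, this is a pilot that openly reports power below the usual 80% and acknowledges its few clusters. That lowers what depends on the figure. It does not justify a formal power statement that the class-level test cannot have, in a protocol that names significance testing as a reason for its layout.

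**Conclusion.** The concern holds. Power of at least 65% at alpha 0.05 together with 0.86 at alpha 0.10 cannot come from a 1-df comparison of three class means: 0.86 implies 54%, and 65% implies 94%. This rests only on the two stated powers, the 2-v-1 layout and the t-test's usual assumptions. It does not depend on the missing difference, the ICC or the meaning of 5 units. Any reading that reconciles the two figures uses more information about between-class variation than three classes provide.

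The actual power is unknown. The 7% to 22% range for effects of 0.5 to 1.0 SD is illustrative and depends on assumed class sizes, effects and ICCs. Separately, the non-parametric option on class means cannot reach 0.05 or 0.10 whatever the effect. The bootstrap floor of 0.25 is conditional on the assumed weights and imposed null, and the missing bootstrap detail is a minor omission in itself.

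**What to change.** In the Statistical Analysis Plan:

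1. Replace the 65% and 0.86 statements with power for two classes against one with 1 between-class df. State which analysis it refers to, the classes per arm entered, the outcome, the difference in scale points, and whether 5 is a variance or an SD.
2. Show the result over a range of ICCs, for example 0.001, 0.01, 0.05 and 0.10, labelled as assumptions.
3. Delete or recompute footnote 1.
4. Add a sentence that the pilot is not powered for a between-arm test and that effects will be reported as estimates with 95% confidence intervals.
5. Drop the non-parametric test on class means, or note that it cannot reach 0.05 with three classes.

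The cost is one short calculation and some SAP wording. No participants or visits are added. The stated power will be less favourable.
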